An MMRM model assumes the KCCQ-TSS data missing at random (MAR). A sensitivity analysis may be performed involving multiple imputation (MI) modeling approach for missing KCCQ-TSS values when the MAR assumption is considered not valid. Implementing the MI process requires 3 steps: 1) each missing value is imputed multiple times, based on statistical modeling, resulting in repetitions of the original dataset, along with the newly imputed values (implemented in the Statistical Analysis System [SAS] using PROC MI); 2) each dataset is analyzed using an MMRM model (implemented in SAS using PROC MIXED). The LS means and SEs from each analysis will be output to a SAS dataset; 3) results from the analyses performed on multiple datasets in step #2 are combined to provide valid statistical inference (implemented in SAS using PROC MIANALYZE).¹

A complete SAS code for MMRM model and implementation of the MI approach described above will be added to the final SAP appendix or to the final study report. Mortality in this short-duration trial is expected to be low and to be comparable between groups and will be ignored in the primary analyses of mean differences in changes in KCCQ total symptom scores, but can be included in the responder analyses (described below) by assigning them to the lowest response (greatest deterioration) category. Should there be a >5% mortality rate in this study, and if it is unequally distributed between treatment arms, then joint modeling of survival and health status (e, g., KCCQ) will be performed. A win-ratio approach^{19,20} may also be considered by analyzing the KCCQ-TSS score as a composite, rank-based outcome, incorporating participant vital status at 12 weeks along with a change in score from baseline to 12 weeks in surviving participants. This essentially is the rank analysis of covariance method, with a corresponding win ratio used to estimate the magnitude of treatment effect.

An exploratory responder analysis will be performed when comparing proportions of participants with a 5- (or 10-) point improvement in the KCCQ-TSS from baseline to Week 12 between the groups. This will be based on a 2-sample difference in proportions test along with a 95% confidence interval for the difference in 2 proportions.

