- Using data from the claims and data on deaths, time to first hospitalization/readmission for heart failure, time to first hospitalization/readmission for other events, and time to death will each be analyzed using a Cox's regression model both for the double-blind treatment period and the entire study duration and include terms for study intervention and stratification factor (HFrEF/HFpEF). Hazard ratios, corresponding 95% CIs, and associated p-values will be presented. Distribution of the times to first hospitalization/readmission for HF, time to first hospitalization/readmission for other events, and time to death will be displayed with Kaplan-Meier curves. Participants who do not experience any such events of interest during the study analysis period will be considered 'censored' in these analyses.

No adjustment for multiplicity will be performed for the exploratory analyses listed above.

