9. HEALTH ECONOMICS

As treatment of participants with symptomatic HF with JNJ-28431754 (canagliflozin) versus placebo may result in lower utilization of hospitalization/readmissions due to HF or other reason, ED visits, the duration of stay at each hospitalization/readmission, and discharge destination will be summarized by each intervention group. Comparison will be made between groups by analyzing differences in hospitalizations/readmissions and ED visits using the Fisher exact test. Descriptive statistics (eg, mean, median, minimum, and maximum) will be provided for the total length of stay in hospitals for each intervention group. Cumulative distribution function of the time to first occurrence of hospitalization/readmission will be estimated by the Kaplan-Meier method and tested using a log-rank test, stratified by the type of HF ejection fraction (ie, HFrEF or HFpEF). In addition, a Cox proportional hazards model with intervention and stratification factor as covariates will be fitted. A point-estimate along with 2-sided 95% CI for HR of the intervention effect (in terms of relative risk reduction (RRR) = $100 \times [1 - \text{HR}] \%$) will be provided. The cumulative event rate derived from Kaplan-Meier estimate will also be displayed graphically to evaluate the timing of event occurrence and the consistency of the treatment effect over time.

REFERENCES

1. Berglund P and Heeringa S. Multiple Imputation of Missing Data Using SAS®. 2014. Cary, NC: SAS Institute Inc. CDISC. “Analysis Data.
4. International Council For Harmonisation (ICH) of Technical Requirement for Pharmaceuticals for Human Use (final version, 2019): ICH Harmonised Guideline – Addendum on estimands and sensitivity analysis in clinical trials (to the guideline on Statistical Principles for Clinical Trials) - E9 (R1).

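### SAP 9 shows first hospitalization by Kaplan-Meier with no rule for deaths, and calls 1-HR a relative risk reduction: two separate, small faults in exploratory analyses.

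*SAP*

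**What the plan says.** SAP Section 9 (Health Economics) sets out the method: "Cumulative distribution function of the time to first occurrence of hospitalization/readmission will be estimated by the Kaplan-Meier method and tested using a log-rank test". Ejection-fraction type is the stratifying factor. A Cox model with intervention and the stratification factor follows, and the hazard ratio is to be given "in terms of relative risk reduction (RRR", defined there as 100 x (1-HR) percent. For the display: "The cumulative event rate derived from Kaplan-Meier estimate will also be displayed graphically to evaluate the timing of event occurrence". Section 9 mentions neither death nor censoring.

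SAP 5.4.2 plans Cox models and Kaplan-Meier curves for time to first hospitalization for HF, time to first hospitalization for other events, and time to death. It covers the double-blind period and the whole study, and results are reported there as hazard ratios. Its censoring rule is: "Participants who do not experience any such events of interest during the study analysis period will be considered 'censored' in these analyses". It does not say how a participant who dies without hospitalization is treated, and it gives no censoring date.

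Death is considered in SAP 5.2.3, but for the KCCQ analysis: "Mortality in this short-duration trial is expected to be low and to be comparable between groups". A change of method is foreseen there: "Should there be a >5% mortality rate in this study, and if it is unequally distributed between treatment arms". Neither document plans a competing-risk estimator for hospitalization.

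**The concern.** Hospitalization is a non-fatal event, and death prevents it. Kaplan-Meier with deaths censored estimates the event probability in a hypothetical setting where those who died could still be hospitalized later. One minus that curve is therefore at least as large as the proportion actually hospitalized. Time to death is an endpoint in its own right, and Protocol 4.1 lists dates of death among the study assessments, so the data to avoid this are already to hand.

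The second matter is one of scale. A hazard ratio compares rates among those still event-free, whereas a relative risk reduction compares proportions with the event by a given time. They nearly agree when events are rare and move apart as events become common. Section 9 covers hospitalization for HF or any other reason, so the event need not be rare. A reader who sets the stated RRR beside the plotted curves would find that the two do not match.

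At stake are the accuracy of a displayed event rate and the wording of an effect measure, not a confirmatory test.

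**Working it through.** **No planned figure to reproduce.** The documents give no hospitalization rate, death rate, event count or target HR for this trial. All rates below are assumptions over about 9 months, shown as ranges.

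**Inputs.**
- HR 0.67 is illustrative: it is the HF-hospitalization hazard ratio that Protocol Section 2 cites from the CANVAS program.
- Anticipated enrollment is 400-480 (SAP 1.4), so 200-240 per arm.
- Assumed Kaplan-Meier risk is 20% or 30%; assumed death risk is 1%, 2% or 5%.

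**Step 1: event rate.** Take constant cause-specific hazards over the period.
- h = -ln(1 - KM) for hospitalization and d = -ln(1 - death risk).
- Cumulative incidence: CIF = h/(h+d) x [1 - exp(-(h+d))].

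Example with KM 30% and deaths 5%: h = 0.3567 and d = 0.0513. Then exp(-(h+d)) = 0.70 x 0.95 = 0.665, and CIF = (0.3567/0.4080) x 0.335 = 29.3%.

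| KM risk | Deaths | CIF | Excess of KM |
|---|---|---|---|
| 20% | 1% | 19.9% | 0.1 point |
| 20% | 2% | 19.8% | 0.2 point |
| 20% | 5% | 19.5% | 0.5 point |
| 30% | 2% | 29.7% | 0.3 point |
| 30% | 5% | 29.3% | 0.7 point |

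The relative excess is about half the death risk. If participants who die were instead kept in the risk set to the end of the period, with no other loss, Kaplan-Meier would equal the CIF and the excess would be zero. The missing censoring rule therefore decides whether this bias exists.

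**Step 2: risk reduction, no deaths.** With control risk p, the treated risk is 1 - (1-p)^HR, and RRR = 1 - [1 - (1-p)^HR]/p.

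Example with p = 20% and HR 0.67: 1 - 0.80^0.67 = 13.9%, so RRR = 1 - 0.139/0.20 = 30.6% before rounding the treated risk.

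| Control risk | 100 x (1-HR) | Risk-scale RRR | Gap |
|---|---|---|---|
| 10% | 33.0% | 31.8% | 1.2 points |
| 20% | 33.0% | 30.6% | 2.4 points |
| 30% | 33.0% | 29.1% | 3.9 points |

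**Step 3: are the two linked?** Adding equal deaths of 5% or 10% per arm at these control risks changes the risk-scale RRR by no more than about 0.1 point. The gap in Step 2 comes from the scale, not from censoring deaths.

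**Step 4: direction.**
- HR 1.25 at 20% control risk: 1-HR is -25%, against -21.7% on the risk scale, so harm is overstated.
- HR 0.80, 5% control risk, deaths 3% (control) and 5% (treated): 1-HR is 20.0%, against 20.4% from the CIFs, so benefit is slightly understated.

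**Step 5: against sampling error.**
- At 20% risk with 240 per arm, the 95% half-width is 1.96 x sqrt(0.20 x 0.80/240) = 5.1 points. A bias of 0.5 point is about one participant (0.005 x 240 = 1.2).
- At 20% control risk, HR 0.67 and 240 per arm, expected events are 240 x 0.20 + 240 x 0.139 = about 81. The standard error of ln(HR) is sqrt(1/48 + 1/33.3) = 0.225. The 95% CI for the HR is about 0.43 to 1.04, so 1-HR runs from -4% to 57%. The labelling gap there is 2.4 points.

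**The case against.** The strongest reply is that this is terminology and a minor display choice. Section 9 prints the definition of RRR beside the label, so a careful reader can see that it is 1-HR. The Cox HR and the log-rank test remain valid as cause-specific analyses. The Kaplan-Meier display is meant to show timing and consistency of effect, and Protocol Section 9 itself names Kaplan-Meier for time-to-event variables. Time to death is reported separately. Mortality is expected to be low, the population is clinically stable at entry, and the endpoints are exploratory without multiplicity control. All of this stands, and it limits the point to a minor one. It does not justify the label, and it does not fill the gap in the censoring rule.

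A reader might go further and infer three things that the documents do not support.
- That SAP 9 itself censors deaths, so its event rates are certainly too high. Section 9 is silent on death; censoring at the date of death is an inference from 5.4.2, which gives no date.
- That both faults always inflate the apparent benefit. Step 4 shows otherwise, and the rate bias raises the displayed rate in both arms.
- That the resource-use results are distorted. The Fisher exact comparisons, counts and length-of-stay summaries in SAP 9 and 5.4.2 do not use Kaplan-Meier.

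**Conclusion.** The point holds as two independent, minor faults.

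1. As written, the 5.4.2 rule also censors participants who die without hospitalization. If that happens at death, the Section 9 curve modestly overstates the proportion hospitalized, by roughly 0.1 to 0.7 point over the assumed rates in Step 1.
2. Calling 100 x (1-HR) a relative risk reduction is a mislabel whether or not anyone dies. When deaths are few or balanced, it lies further from zero than the risk-scale figure, by 1.2 to 3.9 points at HR 0.67 with control risks of 10-30%. It overstates harm when HR exceeds 1.

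These sizes rest on constant hazards, on assumed event and death rates, and on an HR borrowed from another program and for HF hospitalization only. Higher control risks would apply, if at all, to all-cause hospitalization. Both effects are small relative to sampling error at the anticipated enrollment. The analyses are exploratory and outside the fixed-sequence test of SAP 1.3, so no primary or key secondary conclusion changes.

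**What to change.** For the hospitalization endpoints in SAP 9 and 5.4.2:

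- State how and on what date participants who die, or are otherwise lost, leave the risk set.
- Display the cumulative incidence function (Aalen-Johansen) by arm, with death as a competing event, in place of one minus Kaplan-Meier. Kaplan-Meier remains right for time to death.
- Keep the stratified log-rank test and the Cox model, described as cause-specific analyses.
- Report the HR with its 95% CI as a hazard ratio, as 5.4.2 already does.
- Either drop the RRR label, or compute RRR from the arm-specific cumulative incidences at Day 84 and Day 252.

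The cost is a few sentences of SAP text and a standard procedure. Dates of death are already to be collected, so no new data are needed. If deaths would have been censored at death, displayed rates fall slightly in both arms. Any RRR that is retained would usually lie a little closer to zero.

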Appendix 1: The Kansas City Cardiomyopathy Questionnaire (KCCQ)

The KCCQ ([Appendix 1: The Kansas City Cardiomyopathy Questionnaire \(KCCQ\)](#)) is a well-established PRO for use in patients with HF, with published validity and reliability and was recently endorsed by the Center for Devices and Radiological Health (CDRH, US FDA) as a Certified Outcome Assessment through its Medical Device Development Tools Program and is currently under review at the Center for Drug Evaluation and Research (CDER, US FDA).

The Kansas City Cardiomyopathy Questionnaire (KCCQ) is a 23-item self-administered questionnaire developed to independently measure the patient's perception of their health status, which includes heart failure symptoms, impact on physical and social function, and how their heart failure impacts their quality of life (QOL) within a 2-week recall period. This questionnaire requires, on average, 4 to 6 minutes to complete, with a resulting score of 0 to 100, and higher scores indicating better health.

The intent of the study is to enroll participants with NYHA class II and III. As it would be difficult to verify NYHA class with claims and EHR data, the sponsor will use a KCCQ overall summary score at baseline of >40 and <80, which is highly correlated to class II and III in HFrEF and HFpEF based on the research published by Joseph, et al.⁶ In addition to the KCCQ overall summary score, a baseline KCCQ TSS score will also be calculated for each participant.

The 23-item KCCQ quantifies 7 domains of patients' HF-related health status:

- Physical Limitation (6 items)
- Symptom Stability (1 item)
- Symptom Frequency (4 items)
- Symptom Burden (3 items)
- Self-Efficacy (2 items)
- Quality of Life (3 items)
- Social Limitations (4 items)

Item responses are coded sequentially (1, 2, 3, etc.) from worst to best status. Scores are generated for each domain and scaled from 0 to 100, with 0 denoting the worst and 100 the best possible status. In addition, three summary scores are calculated: **Total Symptom score** (average of Symptom Frequency and Symptom Burden), **Clinical Summary score** (average of Physical Limitation and Total Symptoms), and **Overall Summary score** (average of Physical Limitation, Total Symptoms, Quality of Life, and Social Limitation).

Among the 7 domains and 3 summary scores of KCCQ described above, this study will focus on analyzing only two individual domains (physical limitation and quality of life) and three summary scores (clinical summary, overall summary, and total symptom).

Below is a representative example of the scale questions that will be used in this study.

The KC Cardiomyopathy Questionnaire

The following questions refer to your **heart failure** and how it may affect your life. Please read and complete the following questions. There are no right or wrong answers. Please mark the answer that best applies to you.

- Heart failure** affects different people in different ways. Some feel shortness of breath while others feel fatigue. Please indicate how much you are limited by **heart failure** (shortness of breath or fatigue) in your ability to do the following activities over the past 2 weeks.

Place an **X** in one box on each line

Activity	Extremely Limited	Quite a bit Limited	Moderately Limited	Slightly Limited	Not at all Limited	Limited for other reasons or did not do the activity
Dressing yourself						
Showering/Bathing						
Walking 1 block on level ground						
Doing yardwork, housework or carrying groceries						
Climbing a flight of stairs without stopping						
Hurrying or jogging (as if to catch a bus)						

- Compared with 2 weeks ago, have your symptoms of **heart failure** (shortness of breath, fatigue, or ankle swelling) changed?

My symptoms of **heart failure** have become...

Much worse	Slightly worse	Not changed	Slightly better	Much better	I've had no symptoms over the last 2 weeks
					

3. Over the past 2 weeks, how many times did you have **swelling** in your feet, ankles or legs when you woke up in the morning?

- | | | | | |
|--------------------------|---|--------------------------|--------------------------|--------------------------------|
| Every morning | 3 or more times
a week, but not
every day | 1-2 times a week | Less than once a
week | Never over the
past 2 weeks |
|  |  |  |  |  |

4. Over the past 2 weeks, how much has **swelling** in your feet, ankles or legs bothered you?

It has been ...

- | | | | | | |
|--------------------------------|----------------------------------|---------------------------------|-------------------------------|---------------------------------|---------------------------------------|
| Extremely
bothersome | Quite a bit
bothersome | Moderately
bothersome | Slightly
bothersome | Not at all
bothersome | I've had no
swelling |
|  |  |  |  |  |  |

5. Over the past 2 weeks, on average, how many times has **fatigue** limited your ability to do what you want?

- | | | | | | | |
|--------------------------|--------------------------|--------------------------|--|--------------------------|--------------------------|-----------------------------------|
| All of the
time | Several
times per day | At least
once a day | 3 or more times
per week but not
every day | 1-2 times
per week | Less than once
a week | Never over
the past 2
weeks |
|  |  |  |  |  |  |  |

6. Over the past 2 weeks, how much has your **fatigue** bothered you?

It has been ...

- | | | | | | |
|--------------------------------|----------------------------------|---------------------------------|-------------------------------|---------------------------------|--------------------------------------|
| Extremely
bothersome | Quite a bit
bothersome | Moderately
bothersome | Slightly
bothersome | Not at all
bothersome | I've had
no fatigue |
|  |  |  |  |  |  |

7. Over the past 2 weeks, on average, how many times has **shortness of breath** limited your ability to do what you wanted?

- | | | | | | | |
|--------------------------|--------------------------|--------------------------|--|--------------------------|--------------------------|-----------------------------------|
| All of the
time | Several
times per day | At least
once a day | 3 or more times
per week but not
every day | 1-2 times
per week | Less than once
a week | Never over
the past 2
weeks |
|  |  |  |  |  |  |  |

8. Over the past 2 weeks, how much has your **shortness of breath** bothered you?

It has been ...

Extremely bothersome	Quite a bit bothersome	Moderately bothersome	Slightly bothersome	Not at all bothersome	I've had no shortness of breath
					

9. Over the past 2 weeks, on average, how many times have you been forced to sleep sitting up in a chair or with at least 3 pillows to prop you up because of **shortness of breath**?

Every night	3 or more times a week, but not every day	1-2 times a week	Less than once a week	Never over the past 2 weeks
				

10. **Heart failure** symptoms can worsen for a number of reasons. How sure are you that you know what to do, or whom to call, if your **heart failure** gets worse?

Not at all sure	Not very sure	Somewhat sure	Mostly sure	Completely sure
				

11. How well do you understand what things you are able to do to keep your **heart failure** symptoms from getting worse? (for example, weighing yourself, eating a low salt diet etc.)

Do not understand at all	Do not understand very well	Somewhat understand	Mostly understand	Completely understand
				

12. Over the past 2 weeks, how much has your **heart failure** limited your enjoyment of life?

It has extremely limited my enjoyment of life	It has limited my enjoyment of life quite a bit	It has moderately limited my enjoyment of life	It has slightly limited my enjoyment of life	It has not limited my enjoyment of life at all
				

13. If you had to spend the rest of your life with your **heart failure** the way it is right now, how would you feel about this?

Not at all satisfied	Mostly dissatisfied	Somewhat satisfied	Mostly satisfied	Completely satisfied
				

14. Over the **past 2 weeks**, how often have you felt discouraged or down in the dumps because of your **heart failure**?

I felt that way all of the time	I felt that way most of the time	I occasionally felt that way	I rarely felt that way	I never felt that way
				

15. How much does your **heart failure** affect your lifestyle? Please indicate how your **heart failure** may have limited your participation in the following activities over the past 2 weeks.

Please place an **X** in one box on each line

Activity	Severely limited	Limited quite a bit	Moderately limited	Slightly limited	Did not limit at all	Does not apply or did not do for other reasons
Hobbies, recreational activities						
Working or doing household chores						
Visiting family or friends out of your home						
Intimate relationships with loved ones						

Appendix 2: Participant Satisfaction Survey

Appendix 2 provides a representative example of the questions that will be provided to the participant.

For each of the statements below, please indicate your level of agreement:	Strongly Disagree	Disagree	Neutral	Agree	Strongly Agree
Trying something new to possibly treat my heart failure was important to me.					
The virtual study was easy for me to sign up for and get started.					
The Fitbit was easy to set up and use.					
The study app was easy to set up on my smartphone.					
The questionnaires were easy to complete on my smartphone.					
The reminders to complete the questionnaires were helpful.					
The study Fitbit provided helpful information to me.					
It was easy to reach the study team when I had questions or concerns.					
I would recommend participating in a study like this to my friends and family.					

Appendix 3: Schedule of Activities

Period	Screening		Double-Blind Treatment				No Treatment	Notes
	Screening Within 21 days before Day 1	Baseline Within 7 days before Day 1	14±3	28±3	42±3	84±3 End of Treatment		
Day			1 (first dose)				252±7 End of Study	Day -21 to 0=Screening; Day 1 = first dose, Day 84= end of treatment; Day 252=End of Study
Week			2	4	6	12	13-36	Week 12 is equivalent to Day 84 of treatment
Month			0			3	6	Month 3 is equivalent to Day 84 of treatment
Study Procedure								
Screening/ Administrative								
Electronic informed consent ^a	X							
Review medical history	X							
Inclusion/exclusion criteria ^b	X		X					All inclusion/exclusion verification should be completed within the 21- day screening period and before randomization
KCCQ baseline overall summary score <80			X					
Study Intervention Administration								
Randomization			X					
Dispense/administer study intervention			←	→				
Participant-reported adherence via app - weekly			←	→				
Assessments								
KCCQ			X	X	X	X	X ^c	X Kansas City Cardiomyopathy Questionnaire
PGIC			X	X	X	X	X ^c	X Patient Global Impression of Change
PGI-S			X	X	X	X	X ^c	X Patient Global Impression of Severity
Step count and floors climbed							←	→
Claims data collection ^d							←	→

[figure not shown]
Period	Screening		Double-Blind Treatment					No Treatment	Notes
	Screening Within 21 days before Day 1	Baseline Within 7 days before Day 1	14±3	28±3	42±3	84±3 End of Treatment	85-251 ±7		
Day			1 (first dose)					252±7 End of Study	Day -21 to 0=Screening, Day 1 = first dose, Day 84= end of treatment; Day 252=End of Study
Week				2	4	6		13-36	Week 12 is equivalent to Day 84 of treatment
Month			0					6	Month 3 is equivalent to Day 84 of treatment
Participant Satisfaction Survey (optional)								X	
Health Resource Utilization and Health Economics									
HHF for any reason and duration			←					→	Hospitalizations for heart failure
Emergency department visits			←					→	
Readmissions and duration			←					→	
Ongoing Review of Participant Data									
Prohibited medications and new diagnoses			←					→	
Reporting of adverse events*			←					→	

